### **9.3. Secondary Safety Analysis**

The secondary safety objective of this study is to assess the pharmacokinetic profile of ANC-501 capsules in plasma using a sparse sampling model.

#### **9.3.1. Pharmacokinetics**

The secondary endpoint is the plasma concentrations of ANC-501.

Sparse pharmacokinetic (PK) blood sampling will be collected pre-dose and between 0.75 and 2 hours post-dose on Day 1 and between 0.75 and 2 hours post-dose, whenever possible, on Day 8, Day 15, Day 29, Day 43, and Day 56.

Summary statistics (number, arithmetic mean, standard deviation, median, minimum, maximum, geometric mean, geometric coefficient of variation) for the observed PK concentration data will be displayed by scheduled visit for the ANC-501 analyte using the safety population. Reported values marked as Below Limit of Quantitation (BLQ) will be set to 0.5  $\times$  Lower Limit of Quantitation (LLOQ), and reported values marked as Above Limit of Quantitation (ALQ) will be set to 1.0  $\times$  Upper Limit of Quantitation (ULOQ), for summarization purposes. LLOQ is 2.50 ng/mL, and ULOQ is 2,500 ng/mL.

A listing of PK concentration results will also be provided.

Any additional PK summaries, listings, figures, and analyses will be described in a separate analysis plan and performed separately by an external vendor.

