- g. Urine toxicology for selected drugs of abuse (barbiturates, amphetamines, cocaine, opioids,) and breath test for alcohol.
- h. Urine pregnancy test will be conducted only in female subjects of childbearing potential. Female subjects who prematurely discontinue will have a pregnancy test performed at the ET visit.
- i. A blood sample for sparce PK sampling will be collected pre-dose and between 0.75 and 2 hours post-dose at the Day 1 visit and between 0.75 and 2 hours post-dose, whenever possible, at other indicated visits (with the date and time of the previous dose provided by the subject).
- j. A blood sample for exploratory biomarker analysis will be collected in conjunction with PK sampling on Days 1 (pre- post-dose), 8, and 56.
- k. A genetic sample (blood) for exploratory biomarker testing will be collected before the first dose of drug.
- Ophthalmic exam, including slit-lamp imaging, may be performed by an appropriately trained and qualified individual as delegated by the PI and documented in the Study Delegation Log. However, a licensed ophthalmologist or optometrist must oversee this work and will make the determination on subject eligibility as per inclusion criteria #4. Slit lamp imaging of the lens of both eyes will be taken and sent to a central reader for assessment using the LOCS III. Ideally the exam would be performed after cortisol results are known and the subject is otherwise deemed eligible to continue with screening assessments. Additional slit lamp imaging of the lens of both eyes may be performed during the treatment period and sent to a central reader for assessment using the LOCS III, per Investigator's discretion.
- m. The "Baseline/Screening" C-SSRS form will be completed during screening. The "Since Last Visit" C-SSRS form will be completed at any time of day at all subsequent time points.

03 March 2023 Version 6.0 Confidential Page 26 of 63

- n. The Short Form-Health Survey (36-item) (SF-36) weekly. The Hamilton Depression Rating Scale (6-item) (HAMD-6) and the General Anxiety Disorder (7-item) (GAD-7) will be completed up to twice a day for a minimum of three days per week (to achieve 6 collections per week). Subjects will answer EMA orienting questions up to three times per day in conjunction with the other assessments being collected via the EMA application on their cell phones or the provided device.

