- 13. Detectable hepatitis B surface antigen (HBsAg), hepatitis C virus antibody (HCV Ab), or human immunodeficiency virus (HIV) antibody at screening.
- 14. Active psychosis per Investigator assessment.
- 15. Medical history of seizures (does not include isolated febrile seizures of childhood).
- 16. Medical history of bipolar disorder, schizophrenia, and/or schizoaffective disorder.
- 17. History of alcohol or substance use disorder in the 12 months prior to screening.
- 18. Positive alcohol breath test.
- 19. Positive urine drug screen for hallucinogens, psychoactive inhalants, stimulants, opioids, barbiturates, non-prescribed anxiolytics or other non-prescribed sedatives. Does not include positive test for cannabinoids, tobacco or caffeine, unless the subject meets criteria for substance use disorder for these substances.
- 20. Exposure to another investigational medication or device within 30 days or 5 half-lives (whichever is longer) prior to screening.
- 21. Has been previously treated in this study or randomized or treated in any other study employing ANC501 (i.e., subject may not have received study drug and then reenrolled).
- 22. Administration of drugs to treat psychiatric or neurologic conditions that have not been taken at a stable dose for at least 4 weeks prior to day 1.
- 23. Need/plan to take moderate to strong inhibitors and/or inducers of cytochrome P450 (CYP)3A4 (food, beverages, medications, and supplements).
- 24. Any condition not identified in the protocol that in the opinion of the Investigator would confound the evaluation and interpretation of the study data or may put the subject at risk.

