6. STUDY TREATMENT

6.1. Study Treatment Administered

Subjects will receive 50 mg ANC-501 Capsules (5×10 mg capsules) orally once daily at least 1 hour prior to the morning meal for 8 weeks beginning with the first dose administered in the clinic on Day 1.

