## 5. Statistical Methods

The statistical analyses will be reported using tables, listings, and figures (TLFs). Numbering for TLFs will be based on the recommended numbering convention provided by the International Conference on Harmonization (ICH). Continuous variables will be summarized with means, standard deviations, medians, minimums, and maximums unless mentioned otherwise in this statistical analysis plan (SAP). Categorical variables will be summarized by counts and percentage of subjects in corresponding categories. Footnotes will be used to specify the percent calculation when applicable.

Tables will be summarized for scheduled visits, and individual subject data obtained via the electronic data capture (EDC) system and from external vendors may be presented in listings, as indicated in this SAP. If there are multiple readings taken per visit, the most recent reading from that visit will be used in summaries, unless there are pre-dose and post-dose readings taken at the same visit, as mentioned elsewhere in this SAP.

The analyses described in this plan are considered *a priori*, in that they have been defined prior to database lock. Any analysis added after the database lock will be considered post hoc and exploratory. Post hoc analyses will be labeled as such on the output and identified in the CSR. All analyses and tabulations will be performed using SAS version 9.4 or higher. TLFs will be presented in .pdf format. SDTM datasets will be produced using Version 3.3 of the Implementation Guide. ADaM datasets will be produced using Version 1.0 of the Implementation Guide. Upon completion, all SAS programs used to

produce datasets (SDTM, ADaM) and tables will be validated by an independent programmer. The validation process will be used to confirm that statistically valid methods have been implemented and that all data manipulations and calculations are accurate. Checks will be made to ensure accuracy, consistency with this SAP, consistency within tables, and consistency between tables and corresponding listings.

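### The half-LLOQ rule in SAP 9.3.1 makes no exception for the Day 1 pre-dose sample, so the descriptive Day 1 PK summary carries 1.25 ng/mL where the true concentration is zero

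*SAP*

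**What the plan says.** SAP Section 9.3.1 gives one substitution rule for low concentrations: "Reported values marked as Below Limit of Quantitation (BLQ) will be set to 0.5" times the LLOQ. The rule is expressly for summarization, and the section adds that "LLOQ is 2.50 ng/mL, and ULOQ is 2,500 ng/mL". It does not distinguish samples by time point.

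The same section includes a sample taken before any drug is given: "Sparse pharmacokinetic (PK) blood sampling will be collected pre-dose and between 0.75 and 2 hours post-dose on Day 1". Footnote i of the Schedule of Events in Protocol Section 1.3 agrees; samples "will be collected pre-dose and between 0.75 and 2 hours post-dose at the Day 1 visit". Protocol Section 6.1 has treatment "beginning with the first dose administered in the clinic on Day 1".

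The summary statistics, which include the geometric mean and geometric CV, "for the observed PK concentration data will be displayed by scheduled visit for the ANC-501 analyte using the safety population". Section 9.3.1 does not say whether the two Day 1 samples get separate rows. SAP Section 5 uses the latest reading when a visit has several, "unless there are pre-dose and post-dose readings taken at the same visit, as mentioned elsewhere in this SAP".

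Exclusion criterion 21 in Protocol Section 5.2 removes anyone who "Has been previously treated in this study or randomized or treated in any other study employing ANC501".

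**The concern.** Half the LLOQ stands in for an unknown concentration between zero and the assay limit. That is reasonable after dosing, when some drug is expected but cannot be measured. Before the first dose in a drug-naive subject nothing is unknown, because the concentration is zero. The rule as written puts a positive number in its place.

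Plasma concentration is the secondary PK endpoint in both documents. A summary that shows drug in the blood before the first dose is wrong on its face and invites a query. The same sentence leaves a second gap. If a programmer reads the by-visit instruction as one Day 1 row, a set of fixed 1.25 values enters the geometric mean of the post-dose concentrations.

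**Working it through.** The plan states no derived figure to reproduce, so the check applies its rule to the Day 1 samples.

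**Inputs**

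- LLOQ = 2.50 ng/mL and substitution factor 0.5, both from SAP 9.3.1.
- Day 1 samples: one pre-dose and one at 0.75 to 2 hours post-dose, from SAP 9.3.1 and Protocol 1.3.
- Prior exposure: none in eligible subjects, from exclusion criterion 21.
- Number of subjects: at most 20, from SAP 6.1.
- Exceptions elsewhere: none found. SAP 5.1 covers incomplete dates and times, and Protocol 9.4.4 is silent on BLQ values. SAP Section 11 gives the SAP precedence.

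**Step 1: the substituted value.** 0.5 × 2.50 = 1.25 ng/mL.

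**Step 2: separate pre-dose row, every sample BLQ.** All values are identical, so the result is the same for any number of subjects; it was checked for 18 and 20.

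| Statistic (ng/mL unless shown) | SAP rule | BLQ before first dose set to 0 |
|---|---|---|
| Mean, median, minimum, maximum | 1.25 | 0 |
| SD | 0 | 0 |
| Geometric mean | 1.25 | not calculable (log of 0) |
| Geometric CV | 0% | not calculable |

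**Step 3: one pooled Day 1 row.** The documents give no post-dose concentrations, so the values of c below are assumptions that only show the range. With equal numbers of pre-dose values at 1.25 and post-dose values at c, the geometric mean is exp[(ln 1.25 + ln c)/2] = √(1.25 × c), and the arithmetic mean is (1.25 + c)/2.

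| Assumed c (ng/mL) | Pooled geometric mean | Pooled arithmetic mean |
|---|---|---|
| 50 | √62.5 = 7.9 | 25.6 |
| 200 | √250 = 15.8 | 100.6 |
| 500 | √625 = 25.0 | 250.6 |

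The post-dose samples alone would have geometric mean c. Pooling by itself also halves the arithmetic mean, so setting the pre-dose values to 0 is not enough: the two time points must be kept apart.

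**Step 4: can a real pre-dose value hide?** A quantifiable value is at least 2.50 ng/mL, twice the substituted one. Take 20 subjects, 19 at 1.25 and one at 2.50. The maximum rises from 1.25 to 2.50, and the SD rises from 0 to (2.50 − 1.25)/√20 = 0.28. The value stands out.

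**Step 5: reach.** Day 1 is the only visit with a planned pre-dose sample, so rows for Days 8 to 56 do not change under the fix. No test in the SAP uses PK data.

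**The case against.** The strongest case for leaving the text alone is that one uniform, pre-specified rule is transparent and keeps geometric statistics computable in every row. The substitution applies to summaries only, so reported concentrations are not overwritten. The LLOQ is printed beside the rule, so a constant 1.25 with SD 0 can be recognized as a placeholder. It is also only 1.25/2,500 = 0.05% of the upper limit of quantitation. Table layouts are kept outside the SAP, so a separate pre-dose row is an inference. Further PK analyses are assigned to a separate plan that is not available here.

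Most of this stands as a limit on importance. It does not justify the rule for this sample, where the true value is known. Computable geometric statistics have no worth in a row of identical placeholders. That the layout is unspecified does not help either, because both possible layouts give a poor result.

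A reader might go further and infer that the 1.25 floor masks assay carry-over, a swapped sample or undisclosed earlier exposure. The documents do not support that. A quantifiable value would show in the maximum and the SD, and SAP 9.3.1 already plans a listing of PK concentrations, though it does not say how BLQ values will appear there.

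**Conclusion.** The point holds as a minor defect in a stated rule. For an eligible subject, SAP 9.3.1 turns a known zero into 1.25 ng/mL in the Day 1 summary of a secondary endpoint. With separate rows, an all-BLQ pre-dose row shows 1.25 for every measure of location with SD 0. With a pooled row, the Day 1 geometric mean is pulled far below the post-dose value.

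This rests on three assumptions: the subjects meet exclusion criterion 21, the sample is drawn before the dose, and the laboratory reports it as BLQ. The separate row is a reading of SAP Section 5 and is not stated in 9.3.1.

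The consequence stays within descriptive Day 1 PK output. The MADRS and safety analyses are untouched.

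**What to change.** In SAP 9.3.1, state that:

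- BLQ values from samples taken before the first dose are set to 0 for summaries, and the geometric mean and geometric CV are not calculated for that row;
- Day 1 pre-dose and Day 1 post-dose concentrations are summarized separately;
- the number of BLQ samples is shown in each row;
- 0.5 × LLOQ continues to apply to BLQ values after dosing.

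The cost is a sentence or two in the SAP and a small programming change. The only loss is that the pre-dose row has no geometric statistics.

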## **9.4. Exploratory Safety Analysis**

The exploratory safety objectives of this study are to evaluate changes in 12-hour urine, plasma, and saliva cortisol, to evaluate changes in biometrics, and to evaluate biological samples as potential biomarkers and metabolites.

### **9.4.1. Cortisol**

Cortisol sampling (12-hour urine cortisol, plasma and/or saliva cortisol) will be performed at screening and Day 56.

Summary statistics for the observed and change from baseline cortisol level will be displayed at baseline and all scheduled post-baseline visits.

A listing for cortisol level will also be provided. The type of sampling will be included in the listing.

### **9.4.2. Wearable Device Biometrics**

Subjects are to wear their watch-like device throughout the day and night between Day 1 to Day 56 except when charging. The wearable device collects actigraphy data (such as total daily steps, hour with the most steps, waking hour with the least steps, total minutes of sleep divided into daytime sleep and nighttime sleep, resting heart rate, average daily heart rate, and/or heart rate variation) on a daily basis. As the first round of daily data comes after Day 1 dosing, there is no baseline measure.

All wearable device biometric summaries, listings, figures, and analyses will be described in a separate analysis plan and performed separately by an external vendor.

#### **9.4.3. Biomarkers**

Biomarker samples will be collected on Day 1 (pre-dose, post-dose), Day 8, and Day 56.

All biomarker summaries, listings, figures, and analyses will be described in a separate analysis plan and performed separately.

### **10. Tables, Listings, and Figures**

Tables will generally be presented with parameter and visits as applicable in the first column followed by the summary column(s). Descriptive statistics such as mean, median, minimum, and maximum will typically be presented to one decimal place and standard deviation will typically be presented to two decimal places. Numeric laboratory tables may vary for each test depending on the precision of the test.

Listings will be sorted by subject ID and visit within subject ID as appropriate. Data reported in EDC, external vendor data, and/or derived values may be included in the listings, as indicated in this SAP.

Tables, listings, and figures will be maintained outside of this document and may be amended as needed. The spacing, overall presentation, or layout of the displays may need to be altered once data are available.

### **11. Protocol and SAP Differences**

If there are any differences between the study protocol and this SAP, this SAP takes precedent.

